2.3.2 KNOWN POTENTIAL BENEFITS

Participants may experience a number of benefits specific to the perioperative setting. Categories of benefits, with supporting data, are described below:

Cognitive Function

Across various doses and settings, caffeine has been demonstrated to improve arousal, reaction time, vigilance, attention, hedonic tone (e.g., mood), and physical recovery (e.g., ergogenic effects).³⁷ These properties may be particularly useful in the early perioperative setting, where cognitive impairment is common. In fact, data from our preliminary trial suggest that caffeine reduces the incidence of delirium in the PACU concurrent with electroencephalographic evidence of increased neurocognitive arousal.²⁰

Anesthetic Emergence

Caffeine (7.5 mg/kg) has recently been shown to accelerate anesthetic emergence time (~40%) in healthy human volunteers.³⁰ After caffeine administration, participants were also able to participate in psychomotor testing earlier compared to placebo. These findings are supported by basic science data that demonstrate a dose-response relationship in relation to anesthetic emergence acceleration.^{29,62}

Analgesia

Basic science data demonstrate that caffeine confers acute anti-nociceptive properties and protection against hypersensitivity in the days following surgery in both sleep-deprived and non-sleep-deprived rat models.²⁶ Recent Cochrane Reviews have also found that caffeine provided significant analgesic benefit as part of a multimodal strategy in both surgical⁶³ and non-surgical settings.⁶⁴ For obstetric and oral surgery patients, the number needed to treat for achieving at least 50% pain relief (4-6 hours) was 2.2 (1.8 to 2.5), with a relative effect (risk ratio) of 5.5 (3.5 to 8.7).⁶³ Participants receiving caffeine were also less likely to require analgesic re-medication within eight hours (number needed to prevent, 2.9 [2.2 to 4.3]).⁶³ However, data from a single-center randomized trial demonstrate that an intravenous infusion of caffeine, administered prior to anesthetic emergence, did not significantly reduce postoperative pain scores or opioid consumption.²⁰ Lastly, caffeine may also ameliorate rebound perioperative headache, particularly for patients who habitually consume caffeine.²⁵

Thus, there is preliminary evidence – and associated biologic plausibility – to suggest that caffeine may improve postoperative neurocognitive recovery and quality of recovery (e.g., reduced rebound headache).

The Caffeine, Postoperative Delirium, And CHange IN Outcomes after Surgery-2 (CAPACHINOS-2) Study Protocol <2.0>

Version <2.0>
<14 December 2022>

2.3.3 ASSESSMENT OF POTENTIAL RISKS AND BENEFITS

Given the potential benefits of caffeine outlined above, along with the high safety profile described, perioperative caffeine suggests a favorable benefit-to-risk ratio, particularly while observing appropriate eligibility criteria and clinical oversight as proposed in this trial. The study- and site-PIs will review eligibility criteria to ensure appropriate medical screening and trial enrollment.

3 OBJECTIVES AND ENDPOINTS

OBJECTIVES	ENDPOINTS	JUSTIFICATION FOR ENDPOINTS
Primary		
To determine whether intravenous caffeine reduces the incidence of postoperative delirium	--The primary endpoint is delirium, as measured via long-form Confusion Assessment Method (CAM), obtained one hour after PACU admission and twice daily for the first three postoperative days. The CAM will be complemented by a validated chart review method ^{65,66} to mitigate missing delirium assessments.	The CAM is the most widely used measure for identification of delirium worldwide, validated in >22 studies with sensitivity and specificity of >90%. ^{1,67,68}
Secondary		
To determine whether caffeine reduces delirium severity	-- A secondary endpoint will be delirium severity, as measured via the same long-form CAM (CAM-S score).	CAM-S is a continuous scoring metric based on the long-form CAM (scored 0-19, 19 = highest severity). The CAM-S demonstrates high inter-rater reliability (0.88 – 0.92) and strong correlation with important clinical outcomes, including hospital length of stay, cognitive and functional decline, discharge disposition, and mortality. ²
To determine whether caffeine reduces delirium duration	-- An additional secondary endpoint related to delirium will be delirium duration, as measured by the cumulative number of days (n) with a positive delirium screen.	Delirium duration is associated with poor hospital outcomes. ⁶⁹

The Caffeine, Postoperative Delirium, And CHange IN Outcomes after Surgery-2 (CAPACHINOS-2) Study Protocol <2.0>

Version <2.0>
<14 December 2022>

OBJECTIVES	ENDPOINTS	JUSTIFICATION FOR ENDPOINTS
To determine whether intraoperative caffeine improves patient-reported quality of recovery	-- Patient-reported 15-item Quality of Recovery score, ³ which will be assessed in the afternoon on postoperative day two.	The original Quality of Recovery ³³ scale has been used for 20 years in perioperative clinical trials research. Extensive validity, ⁷⁰ reliability, ⁷⁰ and minimal clinically important difference data ³⁵ have been published. This scale was also recently endorsed by the Standardized Endpoints in Perioperative Medicine Initiative. ⁷¹ Caffeine is postulated to ameliorate pain and postoperative confusion, which are each independently associated with poor recovery on this scale. ³⁴
To determine whether caffeine impacts sedation or agitation postoperatively	-- Sedation (-2 to -5), Richmond Agitation and Sedation Scale (RASS). Assessed one-hour after PACU arrival and twice daily. Timing will be aligned with CAM delirium assessment. -- Agitation (+2 to +4), RASS. Assessed one-hour after PACU arrival and twice daily. Timing will be aligned with CAM delirium assessment.	As described in the main text, caffeine enhances arousal via key neurochemical pathways. As such, caffeine may mitigate sedation and states related to hypoactive delirium in the early postoperative setting.
To determine whether caffeine reduces risk of perioperative headache	-- Headache severity (n, 10-centimeter VAS) one-hour after PACU arrival and twice daily. Timing will be aligned with CAM delirium assessment.	Preliminary clinical trial data suggest that caffeine can reduce perioperative rebound headache in habitual caffeine users. ²⁵
To determine the effects of caffeine on postoperative opioid consumption.	-- Cumulative opioid consumption, oral morphine equivalents (mg) from PACU arrival through postoperative day two afternoon.	Preliminary data suggest that intravenous caffeine, administered during

The Caffeine, Postoperative Delirium, And CHange IN Outcomes after Surgery-2 (CAPACHINOS-2) Study Protocol <2.0>

Version <2.0>
<14 December 2022>

OBJECTIVES	ENDPOINTS	JUSTIFICATION FOR ENDPOINTS
		early postoperative recovery, may lead to increased postoperative opioid consumption. ²⁰
Tertiary/Exploratory		
To determine the impact of intravenous caffeine on anesthetic emergence profiles	-- Anesthetic emergence time (minutes; time from surgical closure finish to extubation) -- Time from PACU arrival until PACU discharge criteria met (minutes)	Will help to characterize early postoperative arousal and clinical trajectory
To determine whether caffeine reduces the risk of immediate postoperative pulmonary complications	-- Composite outcome: any occurrence of the following airway/pulmonary complications from extubation through PACU stay: airway adjunct use, unplanned continuous positive airway pressure device, unplanned humidified high-flow oxygen, need for bag-mask ventilation, or reintubation.	Given the arousal effects of caffeine previously discussed, caffeine may plausibly mitigate risk of adverse airway and pulmonary complications in the immediate postoperative setting.
To determine whether caffeine impacts overall hospital length of stay	--Hospital length of stay (days)	Delirium is associated with prolonged hospitalization. If caffeine successfully reduces delirium burden, hospital length of stay may theoretically be reduced.
To determine whether caffeine impacts post-discharge clinical trajectory	--30-day cognitive function (score, n) based on the Montreal Cognitive Assessment --30-day physical function (score, n) based on the PROMIS Physical Function 10a	If caffeine improves outcomes (e.g., delirium, length of stay) during hospitalization, discharge trajectory may also be improved.
To determine whether caffeine impacts discharge disposition	Discharge disposition (e.g., home, skilled care facility)	If caffeine improves outcomes (e.g., delirium, length of stay) during hospitalization, discharge disposition may also be optimized

The CAffeine, Postoperative Delirium, And CHange IN Outcomes after Surgery-2 (CAPACHINOS-2) Study Protocol <2.0>

Version <2.0>
<14 December 2022>

The Caffeine, Postoperative Delirium, And CHange IN Outcomes after Surgery-2 (CAPACHINOS-2) Study Protocol <2.0>

Version <2.0>
<14 December 2022>

4 STUDY DESIGN

4.1 OVERALL DESIGN

The **central hypothesis** of this study is that intravenous caffeine will reduce the incidence of postoperative delirium. This will be a Phase II, single-center, quadruple-blinded, placebo-controlled, block-randomized trial. Written informed consent will be obtained from all participants, and institutional review board approval will be obtained. The trial will follow a parallel design, and participants will be block-randomized with a 1:1:1 allocation ratio (placebo: 1.5 mg/kg caffeine: 3 mg/kg caffeine).

4.2 SCIENTIFIC RATIONALE FOR STUDY DESIGN

This trial will follow conventional (rather than adaptive) methodologies, for the following reason: even if caffeine is not found to reduce risk of postoperative delirium, secondary outcomes (e.g., quality of recovery, headache) may nonetheless suggest benefit and warrant further analysis. Lastly, multiple dosing arms will help to elicit optimal dosing strategies for maximizing the benefit-to-risk ratio across outcomes.

The control group will not receive either caffeine intervention and will remain at standard risk for perioperative complications previously outlined. However, control group patients will nonetheless receive standard perioperative care that would otherwise be received without trial enrollment. Dextrose 5% in water (D5W) was chosen as the placebo intervention, as caffeine citrate is soluble in D5W solution.

4.3 JUSTIFICATION FOR DOSE

The study drug, either caffeine citrate or D5W (placebo), will be administered as an intravenous infusion starting at the beginning of surgical closure and again on the first two postoperative mornings. The infusion will be given over a 30-minute timespan. The two caffeine arms, 1.5 mg/kg and 3 mg/kg were carefully chosen based on preliminary data and literature review. Dosing will be based on total body weight.⁷²

The lower dose of 1.5 mg/kg may be appropriate for such an older population. First, the reduced dose might lower the risk of adverse side effects (e.g., nausea, vomiting, anxiety).³⁶ Second, our preliminary trial was based on a younger population (mean [\pm standard deviation] age [years]: 52 \pm 17), and the cognitive effects of caffeine may be more pronounced in older populations.⁷³ Lastly, serum caffeine concentration increases with age, as the total volume of caffeine distribution is reduced in older patients.⁷⁴ As such, higher peak serum caffeine concentrations are observed with advancing age after both intravenous and oral administration.⁷⁴

The higher dose of 3 mg/kg might provide added cognitive benefit.³⁷ In fact, the mean, weight-based dose for participants receiving caffeine *and not experiencing any delirium* in our preliminary trial was 3 mg/kg.²⁰ Additive cognitive benefit has also been observed with this dose, particularly for domains relevant to delirium (e.g., attention, vigilance)⁷⁵⁻⁷⁸ and after sleep deprivation,⁷⁹ which is commonly experienced in the hospital setting. Nonetheless, this higher dose may also be associated with additional side effects (e.g., anxiety, GI distress, nausea/vomiting), so multiple dosing arms will help to determine optimal perioperative doses that maximize benefit-to-risk ratios across each postoperative day.

4.4 END OF STUDY DEFINITION

The Caffeine, Postoperative Delirium, And CHange IN Outcomes after Surgery-2 (CAPACHINOS-2) Study Protocol <2.0>

Version <2.0>
<14 December 2022>

A participant is considered to have completed the study if he or she has completed all phases of the study including the last visit or the last scheduled procedure shown in the Schedule of Activities (SoA), Section 1.3.

The end of the study is defined as completion of the last visit or procedure shown in the SoA.

5 STUDY POPULATION

5.1 INCLUSION CRITERIA

In order to be eligible to participate in this study, an individual must meet all of the following criteria:

1. Provision of signed and dated informed consent form
2. Stated willingness to comply with all study procedures and availability for the duration of the study
3. Male or female, ≥ 70 years of age
4. Presenting for non-cardiac surgery, non-intracranial neurologic, non-major vascular (e.g., operations below the diaphragm) surgery with planned admission for at least 72 hours.

5.2 EXCLUSION CRITERIA

An individual who meets any of the following criteria will be excluded from participation in this study:

1. Emergency surgery
2. Outpatient surgery
3. Severe cognitive impairment precluding the capacity for informed consent
4. Seizure disorder history
5. Intolerance or allergy to caffeine (based on subjective reporting or objective documentation)
6. Weight >130 kg (as a 3 mg/kg dose would approach the upper limit of daily intake recommended by the FDA)
7. Enrollment in conflicting research study
8. Patients in acute liver failure
9. Acute kidney injury preoperatively
10. Diagnosis of pheochromocytoma
11. Severe audiovisual impairment
12. Non-English speaking

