1 PROTOCOL SUMMARY

1.1 SYNOPSIS

Title:	The CAffeine, Postoperative delirium, And CHange IN Outcomes after Surgery-2 (CAPACHINOS-2) Study
Study Description:	The objective of this study is to test the effects of caffeine on neurocognitive and clinical recovery after major surgery. Specifically, this trial tests the primary hypothesis that caffeine will reduce the incidence of postoperative delirium.
Objectives:	
Primary objective: The primary objective is to determine whether postoperative caffeine reduces the incidence of postoperative delirium, based on standardized delirium assessment methodology.
 
Secondary Objectives: To determine (1) whether caffeine improves postoperative patient satisfaction, based on validated, patient-reported quality of recovery measures, and (2) neural correlates of delirium and Mild Cognitive Impairment, based on advanced electroencephalographic (EEG) analysis.

Endpoints:	
Primary Endpoint: Incidence (%) of postoperative delirium, measured via long-form Confusion Assessment Method (CAM).¹
 
Secondary Endpoints:
 
-- Delirium severity (CAM-S)²-- Delirium duration (days, n)-- Patient-reported 15-item Quality of Recovery score³-- Agitation (via Richmond Agitation and Sedation Scale, RASS)⁴-- Sedation (via Richmond Agitation and Sedation Scale, RASS)⁴-- Headache severity (10-centimeter visual analog scale, VAS)-- Cumulative opioid consumption (oral morphine equivalents, mg)

The CAffeine, Postoperative Delirium, And CHange IN Outcomes after Surgery-2 (CAPACHINOS-2) Study Protocol <2.0>

[figure not shown]
Version <2.0>
<14 December 2022>

Study Population:	In total, surgical patients (n=250; ≥70 years of age) presenting for major non-cardiac, non-intracranial neurologic surgery will be recruited at Michigan Medicine.
Phase:	2
Description of Sites/Facilities Enrolling Participants:	Study operations will be conducted at Michigan Medicine University Hospital and Cardiovascular Center; Ann Arbor, MI USA.
Description of Study Intervention:	This will be a three-arm parallel trial. Participants will be randomized to intravenous dextrose 5% in water (placebo), low-dose caffeine citrate (1.5 mg/kg), or high-dose caffeine citrate (3 mg/kg) at multiple postoperative time points over a 30-minute infusion period.
Study Duration:	The estimated trial duration will be approximately four years.
Participant Duration:	Total study duration for patients will be approximately 30 days.

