1.3 SCHEDULE OF ACTIVITIES (SOA)

	Screening/ Enrollment Visit Day -14 to +1	Day of Surgery Visit 1, Day 1	Visit 2 Day 2 POD1 AM	Visit 3 Day 2 POD1 PM	Visit 4 Day 3 POD2 AM	Visit 5 Day 3 POD2 PM	Visit 6 Day 4 POD3 AM	Visit 7 Day 5 POD3 PM	Day 30
Procedures									
Informed consent	X								
Demographics	X								
Medical history	X								
Randomization		X							
Administer study intervention ^a		X	X		X				
Concurrent medication review	X	X	X	X	X	X	X	X	
Physical exam	X	X	X	X	X	X	X	X	
Vital signs	X	X	X	X	X	X	X	X	
Height	X	X							
Weight	X	X							
Cognitive function	X								X
Delirium assessments	X	X	X	X	X	X	X	X	
RASS Score		X	X	X	X	X	X	X	
Quality of Recovery								X	
PONV		X		X		X			
Headache assessments	X	X	X	X	X	X	X	X	
Opioid consumption data	X	X	X	X	X	X	X	X	
Dietary caffeine intake	X	X	X	X	X	X	X	X	
Physical function	X								X
Safety outcomes		X	X	X	X	X	X	X	X
Hospital length of stay and disposition									X
Adverse event review and evaluation	X	X	X	X	X	X	X	X	X
Complete Case Report Forms (CRFs)	X	X	X	X	X	X	X	X	X

On the day of surgery, assessments will occur one hour after postanesthesia care unit admission. Postoperative day (POD) assessments will occur between 7:00 – 10:00 AM, and afternoon assessments will occur between 3:00 – 6:00 PM. Outcomes will be ascertained either via in-person data collection or chart review as outlined in **Section 8.1, Efficacy Assessments**. ^aA research nurse or physician assistant will oversee the drug administration and monitor blood pressure (every 5 minutes), heart rate, heart rhythm (via 5-lead electrocardiography), and continuous pulse oximetry. ^bSee **Sections 8.2 and 9.4.4** for safety outcomes and assessments. Of note, primary and secondary outcomes are primarily reported in this table. Lastly, the 30-day visit can be conducted virtually and/or by telephone as well.

The Caffeine, Postoperative Delirium, And CHange IN Outcomes after Surgery-2 (CAPACHINOS-2) Study Protocol <2.0>

Version <2.0>
<14 December 2022>

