8 STUDY ASSESSMENTS AND PROCEDURES

8.1 EFFICACY ASSESSMENTS

The specific timing of procedures/evaluations to be done at each study visit are outlined in **Section 1.3, Schedule of Activities (SoA)**. Details regarding major trial assessment measures are described in the following section.

Screening/Enrollment Visit

Screening visits will be performed during either preoperative clinic visits or on the morning of surgery. Trained research team members will make a determination of study eligibility based on medical chart review and concurrent discussion with potential participants. Screening forms will then be reviewed, confirmed, and signed by the study PI ([name]) anytime between the initial screening visit and surgical intervention. During this initial visit, baseline vitals will be taken and a physical exam will be performed by clinic and perioperative clinicians per clinical standards. Baseline research case report forms will be completed, as outlined in **Section 1.3, Schedule of Activities (SoA)**, by trained research team members.

Delirium Assessments

Delirium will be assessed using the long-form CAM, via in-person assessment, during hospitalization. The CAM strategy will be used to assess delirium severity,² and total delirium duration (days) will also be calculated.

Quality of Recovery

The patient-reported 15-item Quality of Recovery scale will be used.³ This scale has been chosen as a key secondary outcome assessment, as caffeine is postulated to reduce delirium and, potentially, headache, which may help with the recovery process. The scale will be administered preoperatively at baseline and on the second postoperative afternoon. Results will be ascertained and recorded via in-person assessment by the research team.

Agitation and Sedation

Given that caffeine enhances arousal, as described previously, caffeine may also prevent states of obtundation, particularly in the early postoperative setting given the possibility of residual anesthesia.

The Caffeine, Postoperative Delirium, And CHange IN Outcomes after Surgery-2 (CAPACHINOS-2) Study Protocol <2.0>

Version <2.0>
<14 December 2022>

The RASS⁴ will thus be used to assess for agitation (+2 to +4) or sedation (-2 to -5) each timepoint of delirium assessment except for preoperative baseline (where the RASS will not be administered).

Headache

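### A preoperative delirium assessment is scheduled, but a positive result affects neither eligibility nor the incidence endpoint, so delirium that predates the drug and persists can count as a postoperative event

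*Protocol*

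**What the plan says.** **Baseline measurement.** In the Protocol, section 1.3, the row "Delirium assessments" is marked in the Screening/Enrollment column, which opens at Day -14. Section 8.1 confirms this when it sets the RASS at "each timepoint of delirium assessment except for preoperative baseline": the preoperative baseline is itself a delirium timepoint.

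**Eligibility.** Section 5.2 lists 12 exclusions, and none names delirium or a positive CAM. Those that bear on it are "Severe cognitive impairment precluding the capacity for informed consent" and "Emergency surgery". Section 5.1 adds "Provision of signed and dated informed consent form".

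**Endpoint.** Section 3 defines the primary endpoint by the long-form CAM "obtained one hour after PACU admission and twice daily for the first three postoperative days". Chart review supplements it, and section 9.1 says this is to pick up episodes on a given day that the in-person CAM missed. Neither section makes an event conditional on a negative baseline.

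**Analysis.** Section 9.3 analyses patients by intention to treat. The covariates that section 9.4.2 offers as examples include the baseline Montreal Cognitive Assessment but not baseline delirium. The model also takes in baseline imbalances with an absolute standardised difference above 0.20.

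**The concern.** An incidence endpoint needs patients who are at risk of a new event. A patient already delirious before surgery is not, and a drug first infused at surgical closure cannot prevent that episode. If such a patient is enrolled and is still CAM-positive in the PACU or on days 1 to 3, the endpoint as written is met.

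Events of this kind fall on all arms and shrink the contrast between them. With about 83 patients per arm, an uneven split of a few cases also shifts the estimate. The protocol plans to collect the information that would prevent this, but attaches no consequence to it. Who may be enrolled is a matter for the protocol, so an SAP could not fully supply the answer.

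**Working it through.** **Inputs.** From section 9.2: N = 250, alpha 0.05, placebo incidence 30% (called baseline there, but meaning the placebo rate), low dose 10-30%, high dose 10-15%, about 10% dropout, stated power 80-95%. From section 9.4.1: two-sided tests. From section 4.1: 1:1:1 allocation. Not in the protocol: the proportion q who are CAM-positive before surgery. It is varied below as an assumption.

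**Sample per arm.** 250/3 = 83.3 randomised. 250 x 0.90 / 3 = 75 after dropout.

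**The plan's own power figure.** With one binary outcome per patient, 75 per arm and a 2-df test of three proportions, a high-dose rate of 10% gives 79-94% (pooled variance) or 82-95% (Wald) across low-dose rates of 10-30%. That agrees closely with the stated 80-95%. A high-dose rate of 15% gives 49-85% or 51-82%, so the full stated range is not reproduced. This does not show the figure to be wrong: the GEE method also needs the number of repeated measures and the within-patient correlation, which are not given. It is a separate matter from this point.

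**Dilution.** If a proportion q is delirious before drug and stays positive in every arm, an incidence p becomes q + (1 - q)p, and a difference d becomes (1 - q)d. For 30% versus 15%:

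- q = 2%: 0.02 + 0.98 x 0.30 = 31.4%; 0.02 + 0.98 x 0.15 = 16.7%; difference 14.7 points.
- q = 4%: 0.04 + 0.96 x 0.30 = 32.8%; 0.04 + 0.96 x 0.15 = 18.4%; difference 14.4 points.

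**Power, high dose against placebo, n = 75 per arm.** The formula is z = [d - 1.96 sqrt(2 m(1 - m)/n)] / sqrt([p1(1 - p1) + p2(1 - p2)]/n), where m is the mean of p1 and p2. For 30% versus 10% with q = 0: m = 0.20, z = (0.200 - 1.96 x 0.0653)/0.0632 = 1.14, so power is 87.2%. The other rows follow in the same way:

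| q (assumed) | Expected cases in 250 | Placebo vs high dose | Difference (points) | Power, cases counted | Power, cases left out and not replaced |
|---|---|---|---|---|---|
| 0 | 0 | 30.0% vs 10.0% | 20.0 | 87.2% | 87.2% |
| 1% | 2.5 | 30.7% vs 10.9% | 19.8 | 85.5% | 86.9% |
| 2% | 5 | 31.4% vs 11.8% | 19.6 | 83.8% | 86.6% |
| 5% | 12.5 | 33.5% vs 14.5% | 19.0 | 78.3% | 85.5% |
| 10% | 25 | 37.0% vs 19.0% | 18.0 | 69.3% | 83.5% |

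For 30% versus 15% the same calculation gives 59.6% at q = 0, 55.9% at 2% and 50.8% at 5%.

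**Chance imbalance.** At 83 per arm one case is 1/83 = 1.2 points, so an excess of two persisting cases moves the crude contrast by 2.4 points. Would the 0.20 rule then bring baseline delirium into the model?

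- 2 versus 0: 0.0241 / sqrt(0.0235/2) = 0.22, above the threshold.
- 3 versus 1: 0.0241 / sqrt((0.0348 + 0.0119)/2) = 0.16, below the threshold.

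The rule covers some two-case imbalances and not others, and only if baseline CAM is among the characteristics compared. Section 9.4.5 does not name it.

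**The case against.** The strongest case on the other side is that the gap is narrow and mostly closed already.

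- **The protocol does not count preoperative delirium as an event.** A reader might infer that it does. The documents do not support that: the baseline CAM lies outside the endpoint window, and a patient counts only if positive again, or still positive, between the PACU and day 3. This stands in full.
- **Other rules remove many such patients.** Participants sign their own consent, and incapacity and emergency surgery are excluded. Section 8.1 places screening at preoperative clinic visits or on the morning of surgery. Section 7.2 lets the investigator withdraw someone who newly meets an exclusion, which would reach loss of capacity. This stands in large part. What remains is mild or fluctuating delirium with capacity retained, including delirium that develops after consent.
- **Randomisation prevents systematic bias.** This also stands. Prevalent cases fall on the arms by chance, so what remains is dilution and chance imbalance, the latter partly handled by the 0.20 rule.
- **The effect is small.** At 1-2% prevalence the loss is about 2-3 points of power for 30% versus 10%. Nothing in the protocol supports 5-10% in consenting, non-emergency patients.
- **The SAP may hold a new-onset definition or a baseline adjustment.** It may, so the lack of such a rule in section 9 is not itself held against the plan. But an SAP cannot change who is enrolled, and dropping baseline-positive patients after randomisation would sit badly with the intention-to-treat statement in section 9.3.

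**Conclusion.** The point holds as a gap in eligibility. The protocol schedules the baseline assessment, is silent on what a positive result means, and defines the endpoint without a new-onset condition. A baseline-positive patient with capacity can be randomised and later scored as an incident case.

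The expected consequence is modest. At an assumed prevalence of 2-4% a 15.0-point difference loses 0.3-0.6 points. For 30% versus 10% at 75 per arm, power drops by about 3 points at 2% and about 9 points at 5%. These figures assume that every prevalent case persists into the endpoint window in every arm. If some resolve, the dilution is smaller. The prevalence is an assumption throughout. The documents do not support a claim that the trial is biased between arms or that its primary result would be invalid. The change is worth making because it is cheap and lets incidence refer to patients at risk.

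**What to change.** Add to section 5.2: *Positive long-form CAM at the preoperative baseline assessment.* Require that result to be reviewed before randomisation, which section 1.3 places on the day of surgery, and report such patients as screen failures under section 5.4, whose definition already fits them.

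Two details of wording matter. The criterion should name the instrument, because the schedule row does not and section 8.1 describes the long-form CAM as used during hospitalisation. It should also stay tied to the preoperative assessment, so that postoperative delirium, which is the endpoint, cannot be read as a newly developed exclusion under section 7.2.

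The cost is a few patients: about 5 per 250 at 2% prevalence. They would be identified before randomisation and could be replaced; even unreplaced, power for 30% versus 10% stays at 86.6% at 2% and 85.5% at 5%. The limit is timing. The schedule has one preoperative delirium assessment, and if it is done at a clinic visit days ahead, delirium that begins later is not caught. Doing that scheduled assessment close to surgery closes this gap; keeping the early one and adding a second would be an extra procedure.
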